7.8.2 Laboratory data

The analyses of laboratory data will be descriptive in nature and will be based on BI standards [\(12\)](#). Note that data from the central Laboratory will be used for all displays described below, unless otherwise specified.

For continuous safety laboratory parameters, normalized values will be derived. Normalisation means transformation to a standard unit and to a standard reference range. The process of normalisation, handling of repeat values at the same visit for by-visit displays, as well as standard analyses for safety laboratory data are described in the BI guidance for the Display and Analysis of Laboratory Data [\(12\)](#). All analyses considering multiple times of the ULN (as described below) will be based on standardized and not normalized values. For continuous safety laboratory parameters, differences to baseline will be calculated. For all outputs, the last assessment before the first treatment at Day 1 is chosen as the baseline value.

Only patients with at least one available post-baseline value will be included in the analysis of an individual laboratory parameter. All individual laboratory data will be listed. Values outside the reference range will be flagged.

For derivation of the last value, the minimum value, and the maximum value, all values during the entire treatment period will be considered under OR. These will be derived for analysis of laboratory, vital signs and local tolerability data. For identification of potentially clinically significant abnormal laboratory values, all values during entire treatment period will also be considered under OR.

Descriptive statistics of laboratory values over time and for the difference from baseline on-treatment (see [Section 6.7](#)) will be based upon normalized values and provided by visit (including follow up) under OC-IR, including summaries of the last value on-treatment, the minimum value on-treatment, and the maximum value on-treatment. Graphical displays via box plots will be produced for the change from baseline, over time, for each continuous laboratory endpoint.

Laboratory values will be compared to their reference ranges; shift tables will be provided for the number of patients with a specific RCTC grade at baseline versus the grade at the last measurement on treatment, as well as the worst grade on treatment. These analyses will be based on standardized laboratory values.

Potentially clinically significant abnormalities will be identified based on BI standard rules which are based on converted lab values, i.e. using SI units. These rules will be listed in the SDL appendix of the CTR. Frequency tables will summarize the number of patients with potentially clinically significant abnormalities. Patients having an abnormal lab value at baseline will be presented separately. A separate listing will present potentially clinically significant abnormal lab values; for each functional lab group all patient's lab values will be listed, if there exists at least 1 lab value with clinically significant abnormality within the group.

The frequency of patients with AST or ALT elevations $\geq 3xULN$, $\geq 5xULN$, $\geq 10xULN$, and $\geq 20xULN$ will be displayed based on standardized laboratory values. To support analyses of liver related adverse drug effects, the frequency of patients with AST and/or ALT $\geq 3xULN$ combined with a total bilirubin $\geq 2xULN$ in a 30 day period after AST/ALT elevation will be displayed, stratified by alkaline phosphatase $< 2xULN$ and $\geq 2xULN$ (a patient can potentially be in both alkaline phosphatase strata in case of multiple AST/ALT and bilirubin elevations). The start of the 30 day time span is triggered by each liver enzyme elevation above the defined thresholds. This analysis will be based on standardized laboratory values.

A graphical analysis of the ALT, AST and total bilirubin during the on-treatment period will also be performed; the so called eDISH plot. In the graph, for each subject, the peak total bilirubin is presented as a fold-increase over the ULN against the peak ALT as a fold-increase over the ULN, on a log₁₀ scale. The measurements displayed of total bilirubin and ALT may, or may not, occur on the same date. Two reference lines, 2xULN for total bilirubin and 3xULN for ALT, are drawn onto the graph in order to divide the plane into 4 quadrants. Normal cases are in the lower left quadrant, potential DILI cases are in the upper right

quadrant (Hy's Law quadrant), while the lower right quadrant is known as the Temple's corollary range (ALT $\geq 3 \times \text{ULN}$ and total bilirubin $< 2 \times \text{ULN}$).

Clinically relevant findings in laboratory data will be reported as baseline conditions (at screening) or as AEs (during the trial) if judged clinically relevant by the investigator, and will be analysed as such.

7.8.3 Vital signs

The analyses of vital signs (blood pressure, pulse rate, body temperature, respiratory rate) and body weight will be descriptive in nature. Descriptive statistics of vital signs over time and for the difference from baseline (see [Section 6.7](#)) will be provided, including the last value, the minimum value and the maximum value during on-treatment period.

Clinically relevant findings in vital signs data will be reported as baseline conditions (at screening) or as AEs (during the trial) if judged clinically relevant by the investigator, and will be analysed as such.

7.8.4 ECG

Abnormal findings in 12-lead ECG will be reported as baseline conditions (at screening) or as AEs (during the trial) if judged clinically relevant by the investigator, and will be analysed as such.

No separate listing or analysis of ECG data will be prepared.

7.9 OTHER ANALYSIS

7.9.1 Biomarker analyses

The following biomarkers will be analysed and reported as a part of the CTR:

- HS-CRP

Results on other biomarkers (e.g. RNA expression, serum and plasma biomarkers) may or may not be reported in the CTR, depending e.g. on the availability of the data. In case they are reported outside the CTR the analysis will be defined in a separate document (in case they are reported in the CTR, the analysis will be described in the CTR).

For the analysis of biomarkers, log transformed data will be used where deemed necessary.

7.9.2 Immunogenicity

Analysis of ADA and assessments of ADA impact on PK will be performed based on the complete administration data of spesolimab from both 1368-0052 and this trial data 1368-0067. Analysis of assessments of ADA impacts on safety and efficacy endpoints will be performed based on this 1368-0067 trial data only for the clinical trial report (CTR).

The ADA status and titre as well as frequency of patients with ADA to spesolimab will be presented by visit. Descriptive statistics of ADA titre (for ADA positive patients, when available) will be provided by visit. The number of subjects with ADA status positive/negative at any time will also be presented. ADA parameters (e.g. treatment-induced ADA positive subjects, transient ADA response and persistent ADA response) will also be presented by visit and cumulatively for the overall study duration. Further exploratory assessments of the ADA data will be performed once data are available and these will be described, if done, in the CTR.

Further analyses based on ADA data will be performed for efficacy-based and safety-based analysis with the following ADA and neutralizing antibody (NAb) status and endpoints.

Patient is considered ADA positive (+) if he/she had at least 1 positive ADA sample in the trial. Otherwise, patient is considered ADA negative (-). Patient is considered NAb positive (+) if he/she had ADA positive and at least 1 NAb positive sample in the trial. Patient is considered NAb negative (-) if he/she had ADA positive but no NAb positive sample OR if he/she is considered ADA negative.

- efficacy-based subgroup analysis as described in [Section 6.4](#)
 - ADA positive and ADA negative subjects (at Week 12 or later time), or
 - Neutralising antibody (Nab) positive and NAb negative subjects (at Week 12 or later time)
- Safety-based subgroup analysis (using e.g. hypersensitivity safety events)
 - ADA positive and ADA negative subjects (at any time), or
 - NAb positive and NAb negative subjects (at any time), or before ADA development (including subjects with events either before their first ADA positive sample or without ADA positive sample throughout) and after ADA development (including subjects with events from the time point of their first ADA positive sample onwards). This approach takes into account the time when ADA actually developed and when the safety event occurred in relationship to ADA.

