There were no relevant changes compared to placebo for laboratory safety, including clinical chemistry, haematology, coagulation parameters, and urinalysis. No clinically relevant changes were observed in 12-lead electrocardiogram (ECGs), vital signs, and cardio-monitoring. Pharmacokinetics (PK) analysis showed that exposure (AUC_{0-tz} and C_{max}) to spesolimab increased with increasing dose in an approximately dose-proportional manner from 0.3 to 10 mg/kg.

The effective half-life of spesolimab is approximately 4 weeks in the linear dose range. Overall, PK data so far suggests target-mediated drug disposition kinetics for spesolimab. Anti-drug antibodies (ADA) were detected in 8 patients, 3 of those had pre-existing levels. Pharmacodynamic (PD) effects in this First in Human Single Rising Dose (SRD) trial [c03361085] were assessed by indirect target engagement of IL36R by spesolimab using an ex-vivo whole blood stimulation assay. Preliminary analyses indicate that $\geq 94\%$ peripheral IL36R receptor occupancy is achieved with doses ≥ 0.05 mg/kg from 30 minutes post infusion to 10 weeks.

In a multiple rising dose (MRD) trial, spesolimab or placebo have been administered to healthy volunteers at multiple ascending i.v. doses of 3, 6, 10 and 20 mg/kg given qw for 4 weeks (i.e. 4 administrations) or a single dose of 20 mg/kg (8 subjects each, 3:1 on active or placebo). Overall, spesolimab was well tolerated. There were no dose dependent AEs, AEs considered to be dose limiting and no SAEs. In all cases the AEs were of mild or moderate intensity. Furthermore, there were no clinically relevant abnormalities on treatment with spesolimab with respect to safety laboratory, vital signs, or ECGs as assessed by a central reader. For further details and most recent results refer to the current Investigator's Brochure (IB) [c03320877-10].

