5. ENDPOINTS(S)

For estimand and handling of missing data and the occurrence of inter-current events, unless otherwise specified, see [Section 6.3](#), [Section 6.4](#) and [Section 6.6](#). For the specification of baseline definition, unless otherwise specified, see [Section 6.7](#).

For the summary of all efficacy data, only those observations which were collected during the on-treatment period will be used.

Baseline for safety data, unless otherwise specified, is the last value prior to initiation of treatment in current 1368-0067 study.

Regarding the analyses of the change from baseline by visit or compared to baseline by visit for efficacy endpoints, unless otherwise specified, we will use last measurement collected prior to initiation of spesolimab as baseline. i.e.,

- For prior spesolimab arm in 1368-0052, the baseline in parent trial is used, which refers to the last measurement collected prior to initiation of treatment in 1368-0052.
- For prior placebo arm in 1368-0052, the baseline in current trial is used, which refers to the last measurement collected prior to initiation of treatment in 1368-0067.

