6.4 SUBJECT SETS ANALYSED

The following analysis sets will be defined for this trial:

Enrolled Set (ES)

This patient set includes all patients who signed informed consent. It will be used for analyses of patient disposition.

Safety Analysis Set (SAF):

This patient set includes all patients who received at least one dose of study drug in trial 1368-0067. This is the main analysis set for efficacy and safety. Patients will be analyzed according to the actual treatment received.

Safety Set ADA (SAF-ADA)

This patient set includes all patients who received at least one dose of study drug and had at least one evaluable ADA sample in trial 1368-0067. This is the main analysis set for ADA impact on efficacy and safety. Patients will be analyzed according to the actual treatment received.

The discussion of all exceptional cases and problems and the decisions on the allocation of patients to populations will be made at the RPM/DBLM at the latest.

Table 6.4: 1 Overview of use of patient analysis sets by class of endpoint and handling of estimand and missing data

Class of endpoint	
	ES SAF
Disposition	OR
Compliance and exposure	OR
iPD	OR
Demographic/baseline characteristics	OR
Concomitant medication	OR
Primary endpoint	OR
Secondary binary efficacy endpoints	OC-NRI: for binary efficacy endpoints
Secondary continuous efficacy endpoints	OC for continuous efficacy endpoints.
Further efficacy endpoints	OC for continuous efficacy endpoints. OC-NRI: for binary efficacy endpoints
Plasma concentration & ADA	OR
Efficacy endpoints by ADA impact	OC for continuous efficacy endpoints OC-NRI for binary efficacy endpoints
AE	OR
Lab data, vital signs	OC-IR

For explanation of the different approaches with regard to missing data see [Section 6.6](#).

[figure not shown]
OC = observed cases excluding values after any use of rescue medication.

OC-IR = observed cases including also values after any use of rescue medication.

OC-NRI = values after any use of rescue medication will be censored and impute with non-responder..

OR = original results.

NRI = Non-Response Imputation, cf. [Section 6.6.2](#).

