6.7 BASELINE, TIME WINDOWS AND CALCULATED VISITS

Measurements reported with date and time and taken prior to start of administration of trial treatment will be considered pre-treatment values. Measurements reported with a date only (and no time) and taken on the day of first administration of trial treatment will also be considered pre-treatment values. These pre-treatment values will be assigned to visits according to the nominal visit number as recorded on the eCRF or as provided by the laboratory.

Baseline, unless otherwise specified, is defined as the last measurement collected prior to the start of administration of the trial treatment.

For the baseline defined in efficacy endpoints like “change from baseline” or “compared to baseline”, unless otherwise specified, is defined as the last measurement before initiation of treatment (cf. [Section 5](#)).

Baseline for time to event endpoints, is defined as the last measurement collected prior to the start of administration of the trial treatment in the current extension trial 1368-0067.

For analysis of anti-drug antibodies (ADA), 2 different baselines will be used for the clinical trial report (CTR). For the analysis of ADA impact on pharmacokinetic (PK), the entire course of treatment is to be considered and assessments prior to initial trial of the parent trial (1368-0052) is considered baseline. Details will be discussed on the trial CTR.

For the analysis of ADA impact on safety and efficacy endpoints, baseline is defined as the first evaluable sample collected prior to treatment administration at baseline of this trial 0067.

Measurements taken after start of administration of trial treatment will be considered either on- or off-treatment values based on the definition in [Section 6.1](#), and will be assigned to visits for statistical analysis, if applicable, as defined below.

Analysis of AE data, potentially clinically significant abnormal laboratory values, concomitant medication or non-drug therapies, as well as use of rescue therapy will not be based on visits. Frequency tables for these data will be using on-treatment data and categorized based on their occurring/starting dates. Therefore, no assignment to time windows will be necessary for such data.

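### ADA safety subgroups and the before/after split count a pre-dose Visit 1 positive as ADA development and use extension-trial samples only

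*SAP*

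**What the plan says.** **Positivity rule.** SAP 7.9.2: "Patient is considered ADA positive (+) if he/she had at least 1 positive ADA sample in the trial". Everyone else is negative. The rule requires neither a post-dose sample nor a rise over baseline. NAb status is built on ADA status.

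**Subgroups.** For safety, SAP 7.9.2 compares ADA (or NAb) positive with negative patients at any time. It also plans a split into before and after ADA development, where the after part starts at the first positive sample. The stated purpose of the split is to respect the time at which ADA really arose. The efficacy subgroups carry a bracketed Week 12-or-later qualifier.

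**Data used.** SAP 7.9.2: "Analysis of assessments of ADA impacts on safety and efficacy endpoints will be performed based on this 1368-0067 trial data only". The same section treats the other ADA work differently: "Analysis of ADA and assessments of ADA impact on PK will be performed based on the complete administration data of spesolimab from both 1368-0052" and the current trial.

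**Baselines.** SAP 6.7 sets two ADA baselines. For PK impact it is the assessment before the parent trial. For safety and efficacy impact, "baseline is defined as the first evaluable sample collected prior to treatment administration at baseline of this trial 0067".

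**Analysis set.** SAF-ADA (SAP 6.4) takes treated patients who "had at least one evaluable ADA sample in trial 1368-0067".

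**Sampling.** The protocol flow chart up to W12 marks ADA/Nab at Visit 1, and its footnote 9 places the pre-dose sample within about an hour before dosing. Visit 1 should preferably coincide with the parent end-of-treatment visit.

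**The concern.** A prior-placebo patient has had no spesolimab when the Visit 1 sample is drawn, so a positive result can only be pre-existing reactivity. The rule still makes the patient ADA positive and starts the after-development period before the first dose. The 0067 baseline in SAP 6.7 was defined for exactly this analysis, but the positivity rule never uses it.

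Prior-spesolimab patients have the opposite problem. Their first exposure was in the parent trial, and their efficacy change is measured from there (SAP 5: "For prior spesolimab arm in 1368-0052, the baseline in parent trial is used"), yet their ADA history before the extension is not used for safety or efficacy impact.

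At stake is the reading of the hypersensitivity analysis, which SAP 7.9.2 names as its example and which concerns an adverse event of special interest. In a trial of about 45 patients, one or two misplaced patients can change what a small ADA-positive group appears to show. The two errors also act on different prior-treatment groups, and prior treatment is how the adverse event tables are displayed.

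**Working it through.** The plan states no ADA rate or sample size for this analysis, so there is no figure to reproduce. The main check applies the rule to typical patients.

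| Patient | ADA history | Class under SAP 7.9.2 (safety) | What happened |
|---|---|---|---|
| A, prior placebo | Positive at Visit 1, no rise later | Positive; all on-treatment events after development | Antibodies pre-date any spesolimab |
| B, prior placebo | Negative at Visit 1, positive later | Positive; split at first positive | Classed correctly |
| C, prior spesolimab | Induced in 0052, still positive at Visit 1 | Positive; all events after development | Classed correctly, because Visit 1 counts |
| D, prior spesolimab | Positive in 0052, negative throughout 0067 | Negative; all events before development | ADA arose in 0052 |
| E, prior spesolimab | Positive in 0052, negative at Visit 1, positive later | Positive, but early events before development | ADA arose in 0052 |

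For patient A this includes a reaction to the Visit 1 loading infusion. The sample precedes the dose, and SAP 7.8.1 assigns any event on the day of first dosing to the on-treatment phase.

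Patient C shows why Visit 1 cannot simply be dropped: that sample is what keeps persisting parent-trial ADA in view. Whether C's antibodies were induced in 0052 or were there before it can be judged only from the parent baseline sample.

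**Scale for patient A (illustration).**

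Inputs:
- Protocol 1.2.1, first-in-human trial: "Anti-drug antibodies (ADA) were detected in 8 patients, 3 of those had pre-existing levels". That trial dosed 78 volunteers, 59 of them with spesolimab. The protocol does not say which denominator applies, so both are used: p = 3/78 = 3.8% and p = 3/59 = 5.1%.
- Number of prior-placebo patients, n: not given. Assumed 11 to 23 of about 45, roughly a quarter to a half.

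Expected number = n × p. Chance of at least one = 1 − (1 − p)^n.

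| n | p | Expected | Chance of at least one |
|---|---|---|---|
| 11 | 3/78 | 0.42 | 35% |
| 11 | 3/59 | 0.56 | 44% |
| 23 | 3/78 | 0.88 | 59% |
| 23 | 3/59 | 1.17 | 70% |

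The rates are imprecise. Exact 95% intervals are 0.8% to 10.8% for 3/78 and 1.1% to 14.1% for 3/59. At the extremes, the expected number runs from 11 × 0.008 = 0.09 to 23 × 0.141 = 3.2.

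**Scale for patients D and E.** The documents give no ADA rates for 1368-0052, so no number can be put on this.

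**The case against.** The strongest reply is that the SAP handles immunogenicity more fully than the positivity rule alone suggests. Several wider readings are tempting and do not hold.

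- *Parent-trial samples are ignored.* They are not: the ADA analysis and the ADA-PK assessment use both trials. The restriction covers safety and efficacy impact in the trial report only.
- *Pre-existing antibodies are reported as a response to spesolimab.* The rule says positive, not treatment-induced. Treatment-induced, transient and persistent ADA are planned as separate outputs, and status is shown by visit. Only the before/after split implies a response. Those outputs do not form the safety subgroups.
- *Efficacy is affected in the same way.* The Week 12 qualifier may keep Visit 1 out of efficacy status. It may instead refer to the efficacy time point; the text does not settle this.
- *All parent-trial ADA is lost.* ADA still detectable at Visit 1 is captured. Only patients D and E are misplaced.
- *The two ADA baselines contradict each other.* SAP 6.7 declares them as separate choices for separate purposes. The conflict is between the positivity rule and the stated aim of the split.
- *The negative group holds many untested patients.* SAF-ADA allows this, but ADA is planned at Visits 1, 2, 3, 5 and 7, in maintenance, and at the end-of-treatment and end-of-study visits. A patient would have to miss every post-dose sample.
- *The 3-of-8 share measures how far an ADA effect is diluted.* It comes from single-dose healthy volunteers. Repeated dosing for two years may give a different mix, and a pre-existing level may still be boosted.

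The public SAP also shows no text for Sections 6.5 and 10, so a finer ADA derivation there cannot be excluded.

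What remains is the safety rule itself: on its wording, patients A, D and E are placed wrongly, and nothing in the readable text corrects this.

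**Conclusion.** The point holds for the safety subgroups and the before/after split. As written, they place a spesolimab-naive patient with pre-existing antibodies after ADA development from the first dose. They also miss, or date late, parent-trial ADA that was undetectable at Visit 1. For efficacy the matter is open until the Week 12 qualifier is explained.

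The size is probably small: about 0.4 to 1.2 prior-placebo patients positive pre-dose, with a 35% to 70% chance of at least one. This rests on carrying over a healthy-volunteer rate and on an assumed arm split. The number of prior-spesolimab patients affected is unknown. The documents support no figure for how much an ADA-positive versus ADA-negative contrast would be weakened.

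The analyses are descriptive, no hypothesis is tested, and the primary endpoint is unaffected. It is still worth correcting, because following the rule literally misassigns events in a planned hypersensitivity analysis.

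**What to change.** In SAP 7.9.2 and 6.7:

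1. For the safety subgroups and the before/after split, define ADA and NAb status as treatment-induced or boosted relative to the last sample before the first-ever spesolimab dose. That is Visit 1 for prior-placebo patients and the parent-trial baseline for prior-spesolimab patients.
2. Include 1368-0052 samples when dating onset in prior-spesolimab patients.
3. Show pre-existing, non-boosted positives on their own line.
4. Do not drop Visit 1 for everyone.
5. State whether the Week 12 qualifier refers to ADA status or to the efficacy time point, and apply the same ADA definition to efficacy.
6. As a minor addition, require at least one evaluable post-dose sample before a patient is classed ADA negative.

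The cost is SAP wording and programming. No new samples are needed: the SAP already plans treatment-induced ADA and already combines the two trials for ADA and ADA-PK. The ADA-positive group may shrink among prior-placebo patients and may grow or shrink among prior-spesolimab patients.

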11. Vital signs will be assessed pre dose as well as 10 minutes post dose. Measurement of pre-dose vitals should precede blood sampling. Vital signs include systolic and diastolic blood pressure, pulse rate, respiratory rate and temperature.
12. Safety laboratory tests include clinical chemistry, haematology, coagulation, and urinalysis and will be performed by the Central Lab.
13. Women of childbearing potential only. Pregnancy testing should be done prior to administration of study drug. Study drug should only be administered in case of a negative test result. In case of a positive urine pregnancy test, a serum pregnancy test will be done.
14. Testing at EoT includes tuberculosis and hepatitis B. Also refer to [Table 5.2.3: 1](#) for information on QuantiFERON testing at Weeks [REDACTED] and [REDACTED]. Please also see [Section 6.2.1.2](#) for further information.
15. After the EoS visit (=individual patient's end of the trial) the investigator should report only any cancers of new histology and exacerbations of existing cancer, trial treatment related SAEs and trial treatment related AESIs of which the investigator may become aware of and only via the BI SAE form, please see [Section 5.2.6.2.1](#).
16. Patient questionnaires should be completed before any other procedures on that day, before the physician assessments, and before study drug administration.
17. Physician assessments should be done after patient questionnaires are completed and before study drug administration. Starting from Week 14, physician assessments, abscess counts, inflammatory nodule counts, non-inflammatory nodule counts, and draining fistula counts are completed every 4 weeks for the next six months, i.e., Weeks 14, 18, 22, 26, 30, 34, 38, and then every 12 weeks thereafter, i.e., Weeks 50, 62, 74, 86, 98. HiSCR is calculated automatically by comparing the lesion count from baseline. Further details are described in [Section 5.1.1](#).
18. Photography should be completed every [REDACTED] weeks starting from Week [REDACTED].
19. PK and ADA/Nab samples are collected at Weeks [REDACTED], EoT, and EoS. Pre-dose PK/ADA/Nab samples will be obtained approximately within 1 hour prior to start of study drug administration.
20. hs-CRP measurements should be completed every [REDACTED] weeks starting from Week [REDACTED].
21. ECG is required every 12 weeks starting from Week [REDACTED].
22. PK and ADA/Nab samples will only be collected if the patient missed the EoT visit collection.

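### ADA and NAb subgroups are defined by any positive sample in the whole trial, so on a plain reading the final analysis groups earlier efficacy and adverse events partly by later antibody status

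*SAP*

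**What the plan says.** SAP 7.9.2 classifies each patient once. For ADA: "Patient is considered ADA positive (+) if he/she had at least 1 positive ADA sample in the trial". For neutralising antibodies: "Patient is considered NAb positive (+) if he/she had ADA positive and at least 1 NAb positive sample in the trial". Everyone else is negative. Neither rule has a time limit.

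These statuses then define two sets of subgroups:

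- **Efficacy:** "ADA positive and ADA negative subjects (at Week 12 or later time"), with a parallel line for NAb.
- **Safety:** "ADA positive and ADA negative subjects (at any time), or" the same for NAb, or a split of events by timing. The first half of that split is "before ADA development (including subjects with events either before their first ADA positive sample or without ADA positive sample throughout"); the second half takes events from the first positive sample onwards. The SAP gives the reason: "This approach takes into account the time when ADA actually developed and when the safety event occurred in relationship to ADA".

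The data source is limited to the extension: "Analysis of assessments of ADA impacts on safety and efficacy endpoints will be performed based on this 1368-0067 trial data only". Sampling continues to the end of follow-up. Footnote 19 of the Protocol flow chart for Week 14 to End of Study reads: "PK and ADA/Nab samples are collected at Weeks [REDACTED], EoT, and EoS". The same flow chart schedules lesion counts and physician assessments at End of Treatment and Follow-up 1, but not at End of Study, 16 weeks after the last dose.

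**The concern.** A subgroup label used to compare outcomes at a given time should rest on what was known by that time. Under an ever/never label, a patient whose only positive sample comes at End of Study, after the last lesion count, belongs to the positive group for every earlier efficacy visit. The label also depends on follow-up: the longer a patient is treated and sampled, the more chances there are for a positive result. This is the setting for immortal-time bias.

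Follow-up here is not independent of response. Protocol 3.3.4.1 has up-titrated non-responders stop treatment if HS-PGA has not improved between Week 12 and Week 24. Time on treatment, and with it the chance of a positive label, can therefore be tied to the efficacy outcome being compared.

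What is at stake is the immunogenicity message: whether antibodies appear to go with loss of response or with hypersensitivity. With about 45 patients and probably few positives, moving two or three patients between groups could change that message.

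**Working it through.** The SAP gives no figure for this analysis and the Protocol has no sample-size calculation (7.5), so there is nothing to reproduce. The documents give no ADA rate, discontinuation rate or response rate for this trial, and the mid-trial sampling weeks are redacted. All rates below are assumptions. A 2-year treatment period is taken as 104 weeks.

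**1. Chance of a positive label by time on treatment.** Assume a constant 10% conversion per 26 weeks. A patient who stops should still attend End of Study 16 weeks after the last dose, so detection runs to 26 + 16 = 42 weeks or 104 + 16 = 120 weeks.

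- Stops at Week 26: 1 − 0.9^(42/26) = 15.7%
- Completes Week 104: 1 − 0.9^(120/26) = 38.5%
- Ratio: 38.5/15.7, about 2.5

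For a range, let c be the cumulative conversion by Week 104, so that P(t) = 1 − (1 − c)^(t/104):

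| c | P(42) | P(120) | Ratio |
|---|---|---|---|
| 20% | 8.6% | 22.7% | 2.6 |
| 40% | 18.6% | 44.5% | 2.4 |
| 60% | 30.9% | 65.3% | 2.1 |

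**2. How many ever-positive patients are still negative at Week 12.** The same formula gives P(12) = 2.5%, 5.7% and 10.0%. The share of Week 104 positives not yet positive at Week 12 is 1 − P(12)/c = 87%, 86% and 83%. If the label covers the whole trial, most of the positive group in a Week 12 table would be there because of later samples.

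**3. Safety, with no true ADA effect.** A simulation of 400,000 patients per scenario assumed:

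- c of 20, 40 or 60%
- discontinuation by Week 104 of 30 or 50%
- adverse event risk over 104 weeks of 20 or 50%
- sampling at Weeks 0, 2, 4, 8 and 12, every 12 weeks thereafter, and at End of Treatment and End of Study

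Results:

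- Crude incidence, ever- against never-positive: risk ratio 1.08 to 1.28 where the truth is 1.
- Share of first events in ever-positive patients that fall before the first positive sample: 49 to 60%.
- Event rate per person-time, after against before the first positive: ratio 0.98 to 1.01.
- Exposure-adjusted rate, ever- against never-positive: ratio 0.99 to 1.01. This follows from the constant event hazard assumed, and it still assigns events that came before antibodies to the positive group.

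**4. Week 12 response, with no true ADA effect and 40% responders.**

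- Discontinuation of 30% in responders and non-responders alike: 40% against 40% by whole-trial status. No bias.
- Discontinuation of 30% in responders and 70% in non-responders: 45.9% against 38.7% (c = 20%), 45.5% against 37.3% (c = 40%) and 44.5% against 34.8% (c = 60%), positive against negative.
- Status taken from samples up to Week 12: 40% against 40% in every scenario.

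**5. The before/after split as written.** It counts subjects with events in two states. Patients who are never positive contribute only to the first state, and converters contribute to both. SAP 7.8.1 defines time at risk for exposure-adjusted rates, but nothing applies it to these two states. Without it, the two counts cannot be compared.

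**The case against.** Several points on the other side stand, and they limit the concern.

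- **Safety timing is addressed.** A reader might infer that adverse events are split only by future status. The SAP does not support that: the before/after split is in the same section and its purpose is stated. The word joining it to the other options may simply enumerate, and the layout, in which the split runs on inside the NAb line, may come from the PDF conversion. The missing NAb wording and the missing denominator remain.
- **The Week 12 qualifier may refer to status.** A reader might take it as settled that a patient first positive at, say, Week 80 counts as positive in a Week 12 table. The bracket could instead say when status is taken, as the parallel bracket in the safety line might. That reading sits badly with the whole-trial definition just above it, so this is an ambiguity to resolve and not proof of an error.
- **The interim is clean.** SAP 3 plans an interim when all patients reach Week 12, and SAP 7 uses data only up to the cut-off. Later samples cannot enter.
- **Direction is not established.** A reader might conclude that the rule favours ADA-positive patients on efficacy and hides hypersensitivity. The first needs discontinuation to depend on response: the Week 24 rule makes some dependence plausible, but no rate is given. The second is unsupported: with no true effect, the crude comparison makes positive patients look worse on safety.
- **Counting treatment weeks alone overstates the gap.** That gives 1 − 0.9^4 = 34% against 10%, or 3.4-fold, but it ignores the End of Study sample. Patients are also sampled at several early visits, so those who stop early are not without data. Patients previously on spesolimab enter already exposed, so zero risk at entry is itself an assumption.
- **Timing is shown elsewhere.** ADA status and titre by visit, and transient and persistent responses, are planned descriptively.

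**Conclusion.** The concern holds in a limited form. The stated definition covers the whole trial, so on a plain reading the final efficacy subgroups and the any-time safety subgroups are formed partly from later antibody status, and longer treatment raises the chance of a positive label. The timing qualifier on efficacy needs clarifying whichever reading was meant. The before/after safety split is the right idea, but it is left as one alternative, does not cover NAb and lacks the denominator that would make it interpretable.

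The size and direction of any bias cannot be derived from the documents. The 2.1- to 2.6-fold difference in the chance of a positive label depends on assumed constant conversion and attendance at End of Study. The efficacy distortion also needs response-dependent discontinuation. These are exploratory, descriptive displays with no hypothesis test, and the primary endpoint does not use them. Severity is low; the change is a cheap improvement.

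**What to change.** In SAP 7.9.2:

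1. State what the Week 12 qualifier refers to. For each efficacy visit, take ADA and NAb status from samples up to and including that visit.
2. Make the before/after-first-positive split the main safety analysis, for ADA and for NAb. Extend the exposure-adjusted method of SAP 7.8.1 to it: events in each state divided by patient-years in that state, with never-positive patients contributing only to the before state.
3. Keep ever/never status as a descriptive row, labelled as whole-trial status.

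The cost is SAP wording and modest programming to divide time at risk at the first positive sample. No new samples or visits are needed. The downside is fewer positive patients at early visits, so some early subgroups may be too small to summarise.
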